#### **5.4 CEST MRI**

- 5.4.1 The largest circular ROI that fits within the brain lesion on axial T1 post contrast imaging will be placed and will define the lesion ROI.
- 5.4.2 The mean signal intensity for a corresponding ROI location on the processed CEST data will be recorded.
- 5.4.3 A mirror ROI will be placed in the contralateral normal appearing white matter on the processed CEST data will be used as the “background” mean signal intensity measurement.
- 5.4.4 An extracranial ROI without visible artifact will be used as the “noise” mean signal intensity measurement.

#### **5.5 Multiple B Value Diffusion Imaging (Adv Diff)**

- 5.5.1 The largest circular ROI that fits within the brain lesion on axial T1 post contrast imaging will be placed and will define the lesion ROI.
- 5.5.2 The AKC for the lesion will be determined using B-values of 0, 1000, and 2000 mm^2/s.
- 5.5.3 The ADC of the lesion will also be determined using B-values of 0 and 1000 mm^2/s.
- 5.5.4 A mirror ROI will be placed in the contralateral normal appearing white matter, and “background” AKC and ADC measurement will be measured.

## 5.6 GESE DSC perfusion imaging – GESE vs GE

- 5.6.1 The largest circular ROI that fits within the brain lesion on axial T1 post contrast imaging will be placed and will define the lesion ROI.
- 5.6.2 The relative cerebral blood volume (rCBV) will be measured for the lesion on both GESE and GE (alone) processed CBV maps with contralateral normal appearing white matter being used as the background (relative).

## 5.7 GESE DSC perfusion imaging – vessel size map

- 5.7.1 The largest circular ROI that fits within the brain lesion on axial T1 post contrast imaging will be placed and will define the lesion ROI.
- 5.7.2 The mean lesion vessel size will be measured with this ROI from the vessel size map.

## 5.8 Adv ASL

- 5.8.1 The largest circular ROI that fits within the brain lesion on axial T1 post contrast imaging will be placed and will define the lesion ROI.
- 5.8.2 This ROI will be used to assess the cerebral blood flow (CBF) from the processed ASL data.
- 5.8.3 A mirror ROI will be placed in the contralateral normal-appearing white matter for assessment of the “background” CBF.
- 5.8.4 This ROI will be used to assess the bolus arrival time (BAT) from the processed ASL data.

# 6 Patient Information Confidentiality Plan

## 6.1 Collection of Identifiers:

The patient identifiers that will be collected in this study consist of patient medical record numbers and dates. Only the PI and collaborators at MD Anderson will have access to the identifiable data. Electronic data will be kept securely at MD Anderson (password protected behind the institution firewall).

The study will be performed in accordance with institutional policies for the use of existing medical information for research. Confidentiality will be maintained throughout the study. No identifying information will be used in any publication from this study. Electronic study data will be stored on password protected institution computers behind the institution firewall. Only the PI and collaborators who have completed Human Subject Protection Training (HSPT) will have access to the study data.

## **6.2 Training of personnel:**

Only MDACC personnel designated by the PI who have completed HSPT training will have access to study records. These personnel will be fully trained to maintain patient health information confidentiality.

## **6.3 Data Storage:**

Electronic study data will be kept on password protected computers behind the institution firewall. Study data will be maintained indefinitely in the future and not be shared, reused or disclosed to anyone or any entity outside of the investigators nor will it be used for other or future research without prior IRB approval. Paper records (data forms, and unique identifiers, etc.) will be kept in a locked file cabinet with access granted only to study investigators and research staff.

## **6.4 Data Sharing:**

Study data will not be shared with any individuals or entities that are not involved in the study without prior IRB approval. Study collaborators will utilize REDCap and Box to store and share data.

## **6.5 Final Disposition of study records:**

After publication, any printed paper records will be placed into the Shred-it confidential waste bins for disposition. The study will be performed in accordance with current institutional standards for the use of existing medical information, banking the data and identifiers for research. There will be no additional use of the study data without prior review and approval by the IRB.

# **7 STATISTICAL CONSIDERATIONS**

## **7.1 Definitions**

Brain metastases “**treatment response**” will be defined by size and contrast to noise ratio (CNR).

Size – treatment response in a lesion will be considered as a decrease in size of 30%. (see section 5.1)

CNR—treatment response will be considered as a decrease in T1 post-contrast CNR of at least 20% (see section 5.2) by standard T1 post contrast imaging for a lesion.

Metastases that do not meet these criteria for treatment response will be considered treatment failure.

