# Proprietary Information of MD Anderson

Protocol No: 2019-1008

Version No: 04

Version Date: August 31, 2021

MRI based on the chemical exchange saturation transfer (CEST) effect from amine, amide, sulfhydryl and hydroxyl protons associated with endogenous metabolites has been shown to provide imaging maps of metabolites in tissue noninvasively. Amide proton transfer (APT) imaging has been developed, which detects amide protons of low concentration in endogenous proteins and peptides in tissue. APT has shown promising results in differentiating radiation necrosis from tumor progression in glioma and necrosis models in rats. APT has also been applied to human glioma patients to differentiate high-grade tumors from low-grade ones with encouraging results. Most germane to this project, the NOE immediately surrounding a brain metastasis one-week following treatment with stereotactic radiosurgery was shown to significantly correlate with tumor volume change at one-month post-treatment. Thus, CEST imaging appears to be a promising tool to help inform future treatment decisions in patients with brain metastasis.

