## 5 Image Analysis

### 5.1 Metastasis size evaluation:

- 5.1.1 A patient must have a single enhancing intraaxial brain metastasis of 5 mm or greater for study inclusion.
- 5.1.2 Metastases will be measured on axial T1 post-contrast imaging on a slice displaying the maximal tumor size using the longest diameter after appropriate magnification on the picture archiving and communicating system (PACS) monitors.
- 5.1.3 Only metastasis planned for radiation therapy will be assessed (for example, lesions present at baseline imaging that are planned for surgical resection will not be assessed).
- 5.1.4 For patients with more than one metastasis appropriate for study assessment, up to ten (10) lesions will be assessed.
  - 5.1.4.1 If there are more than ten lesions present, the five most caudal (lowest) and the five most cranial (highest) lesions that meet evaluation criteria will be tracked.

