## 7.3 Analysis Plan

Patients are expected to have on average four brain lesions each. The primary analysis will be performed on the largest lesion within patients at baseline, and secondary analyses will consider all lesions. The sensitivity of each method at detecting lesions as determined by T1 weighting will be reported with 95% confidence intervals. Analyses will also be performed at the subsequent scans as numbers permit.

For the secondary endpoints that consider treatment response, for each of the imaging methods, at each time point, we will calculate the contrast to noise ratio (CNR) in patients with lesions that respond to treatment and in patients with local failure and will compare these by using a Wilcoxon rank-sum test. If numbers permit, analyses may be repeated using all lesions. Additionally, of the lesions that initially respond, some will subsequently grow in size after the initial response. Of these, some will be considered treatment change and some residual disease. The CNR will be compared between lesions with treatment change and those that are progressive disease using a Wilcoxon rank-sum test.

All statistical tests will be performed with two-sided tests with 5% Type I error rates. No adjustment will be made for the multiplicity of testing. We recognize that the Type I error rate overall will be greater than 5%.

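### The responder-versus-failure comparison cuts two continuous measures, lesion size and T1 post-contrast CNR, and no planned analysis uses the measured changes; adding one is a cheap gain for a secondary endpoint

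*Combined protocol and SAP*

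**What the plan says.** Section 5.1.2 measures size on a continuous scale: "Metastases will be measured on axial T1 post-contrast imaging on a slice displaying the maximal tumor size using the longest diameter". Section 5.2 records the signal values from which T1 post-contrast CNR is formed, also continuous.

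Section 7.1 cuts both. For size: "Size – treatment response in a lesion will be considered as a decrease in size of 30" per cent. For contrast: "CNR—treatment response will be considered as a decrease in T1 post-contrast CNR of at least 20" per cent. It then adds: "Metastases that do not meet these criteria for treatment response will be considered treatment failure". It does not say whether a responder must meet both criteria or only one.

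Section 7.3 takes each method's CNR at each time point "in patients with lesions that respond to treatment and in patients with local failure and will compare these by using a Wilcoxon rank-sum test". Tests are two-sided at 5% without multiplicity adjustment. These are secondary endpoints. Section 7.2 gives no power, effect size, response rate or correlation for them; the 50 patients are justified only by the precision of baseline sensitivity.

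**The concern.** Once the groups are formed, a lesion that shrank by 29% counts on the size criterion the same as one that doubled, and one that shrank by 31% the same as one that nearly disappeared. If a marker is related to the degree of response, the cut discards most of that gradient. The loss grows when one group is small, for instance when local failure is uncommon.

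The comparison has at most one largest lesion from each of 50 patients, and fewer at later scans, because 7.3 analyses those only as numbers allow. A method that does follow response could therefore be reported as showing no difference, although the data to see it had been collected.

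The protocol's own CEST precedent in section 2.5 used an association with measured change: the signal "was shown to significantly correlate with tumor volume change at one-month post-treatment".

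**Working it through.** **The plan's only design figure.** Section 7.2 states a half-width of at most 14.5% for sensitivity with 50 patients. The exact (Clopper-Pearson) 95% interval at 25/50 is 35.5% to 64.5%, a half-width of 14.47%, so the figure reproduces. It has no bearing on the response comparison.

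**Inputs.** From the documents: n = 50 (3.3), largest lesion per patient (7.2, 7.3), rank-sum test, two-sided 5% (7.3). Assumed, because the documents are silent: the correlation ρ between marker and response, the share responding f, and normality.

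**Step 1: size-only cut, smooth relation.** Let x be standardised size change and the marker y = ρx + √(1−ρ²)·e, with e standard normal. A lesion responds if x exceeds the normal quantile at 1−f.

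- Rank-sum: z = |W − n₁(n+1)/2| / √(n₁n₀(n+1)/12), significant above 1.96.
- Spearman: t = r√((n−2)/(1−r²)) on 48 degrees of freedom.

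Power from 20,000 simulated trials per cell (differences use unrounded values):

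| ρ | f | Rank-sum | Spearman | Loss, points |
|---|---|---|---|---|
| 0.3 | 50% | 37.3% | 52.7% | 15.4 |
| 0.3 | 70% | 34.4% | 52.4% | 18.0 |
| 0.3 | 85% | 25.5% | 51.9% | 26.4 |
| 0.4 | 50% | 61.6% | 79.3% | 17.8 |
| 0.4 | 70% | 55.9% | 78.7% | 22.8 |
| 0.4 | 85% | 42.9% | 79.2% | 36.2 |
| 0.5 | 50% | 82.8% | 94.8% | 12.0 |
| 0.5 | 70% | 77.4% | 94.5% | 17.2 |
| 0.5 | 85% | 62.6% | 94.9% | 32.3 |

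The range is 12 to 36 points. A separate, smaller run (1,500 trials per cell) reached 38, hence about 12 to 38. With ρ = 0, both tests reject in about 5% of trials. With 30 patients the loss over the same range is 11 to 41 points. Widening to ρ of 0.2 to 0.6 and f of 50% to 90% at n = 50 gives about 4 to 49 points for correlation tests generally.

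**Step 2: the marker changes only at the cut.** Let the marker be shifted by 0.6 to 1.0 standard deviations in responders and otherwise be unrelated to size change, with 50% to 80% responding. The rank-sum test now has more power than Spearman, by 11 to 32 points.

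**Step 3: both criteria.** Section 7.1 also uses CNR, so step 1 is not the plan's exact comparison. Take n = 50, an assumed correlation of 0.3 between size change and CNR change, and each criterion met by 50% or 70%:

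| Marker correlation with size / CNR change | Spearman on size alone versus rank-sum |
|---|---|
| 0.4 / 0.4 | better by 7 to 9 points (both required) or 10 to 27 (either) |
| 0.4 / 0.2 | better by about 33 to 47 points |
| 0.2 / 0.4 | worse by 4 to 22 points |

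In a further run, size alone was worse by up to about 23 points when the marker followed CNR more than size. By contrast, Spearman on the combined ranks of size change and CNR change beat the rank-sum test in every n = 50 cell run, by about 17 points or more, whether both or either criterion was required. Step 3 again assumes a smooth relation.

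**The case against.** The strongest case against is that a responder definition is a legitimate clinical summary, that the analysis is secondary and openly unadjusted, and that no power was promised. This stands, and it is why the point is an improvement and not an error. The absence of a cited source for the cut is not itself a fault.

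It is also true that most treatment-response objectives in 1.2.2 (CEST, Adv Diff, GESE DSC, Adv ASL) ask about radiation necrosis versus progression. That is a two-class question, and a correlation with size change does not answer it. The point is therefore confined to the responder-versus-failure comparison in 7.3.

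The precedent in 2.5 is narrow: one CEST signal around the lesion at one week, against volume change at one month. It shows that the measured scale is usable, not that every method will relate smoothly to diameter.

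A reader might infer that this plan loses a fixed 12 to 38 points. The documents do not support that: they give neither the correlation nor the response rate, and the range describes a size-only cut under a smooth relation. A reader might also infer that percent size change should simply replace the responder split. Step 3 shows that this can lose power, because it drops the CNR half of the definition.

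Finally, lesions may respond and then regrow (7.1, 7.3), and a vanished lesion has no region of interest under 5.2 to 5.8. Both are real gaps in any bare proposal to correlate, and the fix has to close them.

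**Conclusion.** The concern holds in a limited form. Two continuous measures are cut, the groups are compared by a rank-sum test, and nothing planned uses the measured changes. Where the marker varies smoothly with response, power is lost. The figure of about 12 to 38 points rests on n = 50, a size-only cut, bivariate normality, correlation 0.3 to 0.5 and 50% to 85% responding. The size under the two-criterion definition cannot be fixed from the documents, and a pure threshold effect would favour the planned test.

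This is a cheap improvement to a secondary endpoint. It gives no reason to doubt the primary sensitivity analysis or the sample size.

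**What to change.** In 7.3, for the responder-versus-failure comparison only:

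- Prespecify a Spearman correlation with 95% CI between each method's value and measured response in the patient's largest lesion. Use both percent change from baseline in longest diameter and percent change in T1 post-contrast CNR, for example as the sum of their ranks, and report each separately as well.
- State which scan's marker value is paired with which scan's change, across the eight scans in 4.5 and 4.6, so that a regrown responder is not confused with a lesion that never responded.
- Score a vanished lesion as −100% size change only where a marker value exists, such as from an earlier scan. State how its CNR change is handled, since it too needs a region of interest.
- If all lesions are analysed, use a patient-level cluster bootstrap.
- Keep the responder/failure rank-sum comparison as the clinical summary, and state in 7.1 whether both criteria or either defines response.
- Leave radiation necrosis versus progression as a two-group analysis.

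The cost is SAP wording and a few lines of code, with no new scan, reader or patient. The downside is that a correlation is less directly clinical and can miss a pure threshold effect; the retained responder split covers that.

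### Treatment response is partly defined by a fall in T1 post-contrast CNR, with no rule joining it to size, and CNR is then compared between the response groups, so for T1-related methods the groups can differ partly by construction.

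*Combined protocol and SAP*

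**What the plan says.** Section 7.1 (Definitions) opens by stating that treatment response "will be defined by size and contrast to noise ratio (CNR"). Two separate statements follow, and each calls its own criterion a response:

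- Size: "treatment response in a lesion will be considered as a decrease in size of 30" per cent.
- CNR: "a decrease in T1 post-contrast CNR of at least 20" per cent, measured on standard T1 post-contrast imaging.

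The section then says: "Metastases that do not meet these criteria for treatment response will be considered treatment failure". It does not say whether failing one criterion is enough or both must fail.

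The same section makes initial responder status a condition for calling a lesion recurrent on imaging. Lesions that grow without meeting the recurrence criteria are labelled radiation necrosis.

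Section 7.3 (Analysis Plan) sets out the treatment-response comparison: "we will calculate the contrast to noise ratio (CNR) in patients with lesions that respond to treatment and in patients with local failure". This is to be done "for each of the imaging methods, at each time point", and the analysts "will compare these by using a Wilcoxon rank-sum test". Nothing exempts T1-related measures or acknowledges the overlap with Section 7.1.

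Quantitative MRI, including idealized T1, is one of the study sequences (Sections 1.2.2.1, 4.3 and 5.3). Sections 5.2 to 5.8 all define the lesion ROI on the axial T1 post-contrast image.

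**The concern.** A lesion enters the responder group partly because its T1 post-contrast CNR fell. Responders will therefore tend to have lower T1 CNR at follow-up, and higher T1 CNR at baseline, whatever happened to the tumour. Any CNR that tracks T1 post-contrast CNR inherits part of that difference. A significant result for such a method could reflect the group definition and say nothing about shrinkage. The plan's caveat on multiplicity does not cover this, because the problem arises within a single test.

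The missing joining rule is a second problem. Two analysts could follow the plan faithfully, classify lesions differently and report different results. The label also carries forward. Take a lesion that halves in size, keeps its CNR and later regrows by 40% at one scan, with no pathology available. If both criteria are required it was never a responder, so it cannot be recurrent and becomes radiation necrosis. If either criterion suffices, it is recurrent disease. The same choice decides which lesions enter Section 7.3's later comparison of treatment change with progression, which is limited to initial responders.

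**Working it through.** **Is there a figure in the plan to reproduce?** Not for this comparison. The only computed design figure is the 14.5% half-width in Section 7.2. The exact 95% interval at 25/50 is 35.5% to 64.5%, half-width 14.47%, which reproduces it. It concerns the primary sensitivity estimate. No power or precision is given for the response comparison.

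**Inputs from the documents:** 50 patients, with the largest lesion used in the primary analysis; a 30% size criterion; a 20% T1 CNR criterion; a two-sided rank-sum test at 5%.

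**Assumptions, none in the documents:** log T1 CNR has SD 0.4 at baseline and at follow-up; baseline/follow-up correlation c = 0.6; median CNR ratio 0.8; median size ratio 0.7; SD of log size ratio 0.35; size change independent of CNR. The tested CNR has correlation rho with T1 post-contrast CNR at the same scan and no link with size change.

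**Step 1: level and change.** Section 7.3 tests CNR at each scan, which is a level. Section 7.1 uses the change, follow-up minus baseline on the log scale. With equal variances, the correlation of the follow-up level with the change is √((1 − c)/2) = √(0.4/2) = 0.45. For the baseline level it is −0.45. A method with correlation rho to the follow-up level has correlation 0.45 × rho with the change, so 0.9 gives about 0.40. The overlap is real but diluted.

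**Step 2: rejection rate at nominal 5%** (50 lesions, 2,000 simulated trials per cell, follow-up CNR):

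| rho | both criteria | either criterion | size only |
|---|---|---|---|
| 0 | 6% | 5% | 5% |
| 0.3 | 7% | 7% | 4% |
| 0.5 | 9% | 10% | 4% |
| 0.7 | 16% | 16% | 5% |
| 0.9 | 23% | 25% | 4% |

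The simulation standard error near 5% is √(0.05 × 0.95/2000) = 0.5 points, so the small departures at rho 0 and in the size-only column are noise. Baseline CNR gives similar rates in the opposite direction (22–24% at rho 0.9).

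**Step 3: sensitivity to the assumptions.** For T1 CNR itself (rho = 1) the rate is 27–29% with 50 lesions and 18% with 30. If the follow-up SD is 1.5 times baseline, the level–change correlation becomes (2.25 − 0.6 × 1.5)/(1.5 × √(2.25 + 1 − 2 × 0.6 × 1.5)) = 1.35/(1.5 × 1.204) = 0.75, and the rate reaches 72%.

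**Step 4: joining rule.** Suppose each criterion is met by 50% of lesions, independently. Requiring both gives 0.5 × 0.5 = 25% responders. Accepting either gives 0.5 + 0.5 − 0.25 = 75%. Half of the lesions change group. With each rate between 30% and 70%, 42% to 58% change group. Positive correlation between the criteria would lower this.

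**The case against.** **Reach.** Standard T1 post-contrast CNR is the reference and is not itself a study sequence under test. The only T1-based study method is quantitative MRI, and its response objective (Section 1.2.2.1) is a trend in T1 and T2 values against normal brain. Sections 5.5 to 5.8 record diffusion, perfusion and flow measures with no noise ROI, and the documents give no correlation of these with enhancement. This stands as a limit: the effect is near nil for a method uncorrelated with T1 CNR. It does not remove the point, because Section 7.3 tests CNR for every method without exception.

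**Meaning of a false positive.** For a method other than T1 CNR, association with a reference that contains T1 CNR is a genuine association with response as the protocol defines it. That is fair. The rates above are false-positive rates only with respect to shrinkage. What remains is that the plan cannot tell the two apart.

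**Reason for including CNR.** Section 2.1 says that size change on contrast-enhanced T1 imaging is not, by itself, specific to cell death. That is a reason to keep the two-part definition, and the documents do not support the inference that size alone should replace it.

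**Stronger readings a reader might infer.**

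- *Rejection rates of 38% or 82%.* These arise at correlations of 0.5 and 0.8 with the change in T1 CNR when both criteria are required. Section 7.3 compares levels, and under equal variances with c = 0.6 even T1 CNR itself correlates only 0.45 with its own change.
- *Lesions that neither shrink by 30% nor grow are failures under any reading.* If either criterion suffices, such a lesion with a 20% CNR fall is a responder.
- *The necrosis-versus-progression test is circular in the same way.* That split rests on pathology or size growth. T1 CNR enters only through the initial responder requirement.
- *There is no joining rule at all.* The opening sentence favours requiring both, so the rule is ambiguous and not absent.

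**Conclusion.** The concern holds in a limited form. Following Sections 7.1 and 7.3 as written gives a partly circular test for T1-related CNR, and for other CNR measures in proportion to their correlation with T1 post-contrast CNR. Only the direction follows from the documents. Under the stated assumptions the inflation is slight at a correlation of 0.3 and reaches about four to five times nominal at 0.9 (23–25% against 5%). It could be larger if CNR varies more after treatment than before, and smaller with fewer lesions.

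The joining rule matters separately. In the 50/50 illustration it moves responders from 25% to 75%, and it also decides which lesions can be called recurrent. These are secondary comparisons. The primary baseline sensitivity analysis and its 14.5% precision are unaffected.

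**What to change.** 1. In Section 7.1, state whether a lesion must meet both criteria or either one to be a responder, and what a lesion meeting only one is called. Reconcile this with the recurrence and radiation-necrosis rules in the same section.
2. In Section 7.3, keep the protocol's response definition, but also run each CNR comparison with groups formed by the existing size criterion alone.
3. Base any claim about T1-related or enhancement-correlated CNR on that CNR-free grouping, and label the result from the CNR-inclusive grouping as partly circular. Each method's observed correlation with T1 post-contrast CNR would show which methods this covers.

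The cost is a wording change and one further analysis of data already collected. The downside is that lesions changing only in CNR do not count as responders in the CNR-free grouping.

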## 4.5 Imaging Time Points

- 4.5.1 The baseline study scan will be performed within the fourteen (14) days **before** scheduled brain radiation treatment.
- 4.5.2 Seven additional study scans will be performed on the schedule of the patient's clinical protocol, but not less than four (4) weeks apart and not more than 16 (sixteen) weeks apart.

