## 4.6 Conclusion of Study Participation:

- 4.6.1 Completion of eight (8) study scans.
- 4.6.2 Upon patient request.
- 4.6.3 A contraindication to further MR imaging.
- 4.6.4 Death.

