# Proprietary Information of MD Anderson

Protocol No: 2019-1008

Version No: 04

Version Date: August 31, 2021

Disease **recurrence** will be determined by surgical pathology (if available) or at least three months of imaging follow-up. Imaging findings will be considered recurrent disease in a lesion if:

1. The lesion was originally considered to be a treatment responder.
2. The lesion showed a successive increase in the size of 25% from nadir or a single imaging time point increase of 40%. (see section 5.1)

Lesions that show an increase in size, but do not meet these criteria will be considered radiation necrosis.

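### Section 7.1 makes treatment failure the residual class with no evaluability condition, so lesions of patients who leave early enter the secondary CNR comparisons as failures

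*Combined protocol and SAP*

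**What the plan says.** Section 7.1 of the combined protocol and SAP defines response by two changes from baseline. For size, "treatment response in a lesion will be considered as a decrease in size of 30" percent; for CNR, "treatment response will be considered as a decrease in T1 post-contrast CNR of at least 20" percent. However the two are combined, each needs a measurement after radiosurgery. The section then closes the classification: "Metastases that do not meet these criteria for treatment response will be considered treatment failure". It names no third class.

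Section 4.5 puts the baseline scan within the 14 days before radiation and adds that "Seven additional study scans will be performed on the schedule of the patient's clinical protocol, but not less than four (4) weeks apart", with an upper limit of 16 weeks between scans. Section 4.6 ends participation after eight scans, but also by death, "Upon patient request", or on "A contraindication to further MR imaging". It requires no minimum follow-up.

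Section 7.3 uses the classification. For every imaging method, and separately at every scan, the plan states: "we will calculate the contrast to noise ratio (CNR) in patients with lesions that respond to treatment and in patients with local failure". These groups are compared by a Wilcoxon rank-sum test at two-sided 5%. The section allows some analyses to depend on numbers, which governs whether they are run. It does not say how an unassessed lesion is classed.

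**The concern.** A residual class absorbs whatever was not observed. A patient who has the baseline scan and then dies of extracranial disease, withdraws, or can no longer have MR has no follow-up size or CNR. The lesion has not met the response criteria, so the rule labels it a failure although nobody saw local failure. Such a lesion still has a baseline CNR, and perhaps an early one, so it can enter the failure arm of the section 7.3 tests at those scans.

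A related case is the lesion measured once, very early, before a response could reasonably be expected. Section 7.1 gives no time at which response is judged, so this lesion is also a failure.

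The failure arm then mixes observed failures with early exits. If exit is unrelated to response, the mixture pulls the comparison towards no difference. If exit goes with poor general condition, the comparison may instead reflect that.

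**Working it through.** **1. The plan's own figure.** The only computed figure is the 14.5% in section 7.2. The exact binomial 95% interval at 25/50 runs from 35.5% to 64.5%, that is ±14.47%, so it reproduces. It belongs to the primary sensitivity and does not depend on how failure is defined. The plan gives no figure for the response comparisons.

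**2. The text side by side.** Response needs a follow-up measurement (7.1). Exit can come before any follow-up (4.6). Everything short of response is failure (7.1). The failure group is tested at each time point (7.3). No section defines an evaluable lesion, a minimum number of follow-up scans, an assessment time, or the handling of death, withdrawal or missed scans.

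**3. How early one scan can be.** Baseline may be 2 weeks before radiation and the next scan 4 weeks after baseline: 4 − 2 = 2 weeks after radiation.

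**4. Which tests are touched.** The Wilcoxon test needs a CNR value at the scan in question. A baseline-only lesion enters only the baseline test. A lesion that leaves after the second scan enters the first two.

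**5. Illustration for a test in which every unassessed lesion has a value, such as baseline.** From the documents: n = 50 patients, one largest lesion each, two-sided 5%. Assumed, because the documents are silent: response r = 0.70 whether or not the patient leaves; true AUC 0.75; k = 5, 10 or 15 unassessed lesions.

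- Observed responders R = r(n − k); observed failures F = (1 − r)(n − k)
- Failure group under the rule = F + k
- Would-be responders in it: m = rk/(F + k)
- Observed AUC = 0.75(1 − m) + 0.5m = 0.75 − 0.25m
- Power ≈ Φ[(AUC − 0.5)/SE − 1.96], with SE = √[(R + G + 1)/(12RG)] and G the size of the failure group used

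| k | R | F | F + k | m | AUC | Power, labelled failure | Power, excluded |
|---|---|---|---|---|---|---|---|
| 5 | 31.5 | 13.5 | 18.5 | 3.5/18.5 = 19% | 0.703 | 66% | 75% |
| 10 | 28 | 12 | 22 | 7/22 = 32% | 0.670 | 54% | 70% |
| 15 | 24.5 | 10.5 | 25.5 | 10.5/25.5 = 41% | 0.647 | 43% | 64% |

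For k = 10 under the rule, SE = √[51/(12 × 28 × 22)] = 0.083, and 0.170/0.083 − 1.96 ≈ 0.09, so power is 54%. With exclusion, SE = √[41/(12 × 28 × 12)] = 0.101, and 0.25/0.101 − 1.96 ≈ 0.52, so power is 70%.

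The formula uses the null variance and is approximate. Two simulations of 4,000 runs gave, for k = 5, 10 and 15, power of 66–69%, 55–56% and 42–48% under the rule, and 78–80%, 74% and 66–67% with exclusion. Simulated AUC was 0.70, 0.67 and 0.65–0.66.

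**6. Range over the assumptions (same formulas).**
- Mildest (50% response, 5% unassessed): m = 1.25/26.25 = 5%, AUC 0.738, power 82% against 84% with exclusion.
- Most severe (85% response, 30% unassessed): m = 12.75/20.25 = 63%, AUC 0.593, power 20% against 44%.

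**The case against.** The strongest reply is that both criteria are measured changes, so the residual sentence can be read as covering measured lesions only. Section 7.3 also speaks of local failure, which ordinarily means something observed. A careful analyst might well proceed that way. But no text makes that restriction, section 7.1 supplies the only definition of failure, and the choice would be made with the data in hand.

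It is also fair that a lesion measured once at two weeks is not missing data. The gap there is the absent assessment time. That distinction stands, although one rule can settle both. It stands too that the tests are secondary and openly unadjusted for multiplicity, and that the magnitudes rest on assumed inputs.

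Three stronger readings are tempting and not supported:

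- *The local failure rate is overstated.* Section 7.3 plans no estimate of that rate.
- *The study closes before recurrence can be judged.* Section 7.1 says recurrence "will be determined by surgical pathology (if available) or at least three months of imaging follow-up". At the minimum spacing, scan 8 falls at 7 × 4 = week 28, leaving 12 weeks after growth first seen at week 16. But intervals may be as long as 16 weeks, the start of the three months is not stated, and pathology is an alternative route.
- *A stated objective of predicting response is compromised.* Section 1.2.2 lists T1 and T2 trends and the separation of necrosis from progression. Prediction appears only as background motivation.

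**Conclusion.** The point holds for the secondary responder-versus-failure comparisons. It is more than missing detail: section 7.1 states a catch-all rule that, followed literally, gives the wrong label to lesions nobody could assess. The size cannot be known from the documents. In the central illustration the loss is modest with 5 unassessed lesions and material with 10 to 15; across the assumed range it runs from negligible to severe. Exclusion is less biased and more powerful in that illustration, but this depends on exit being unrelated to response. If the two are related, exclusion can also bias the result, so exits need to be reported by reason. The change should be made before the response analyses are run.

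**What to change.** In section 7.1, state that response and failure are both assigned only to lesions with a post-radiosurgery assessment at or beyond one prespecified time, the same for both classes. The three months that section 7.1 already uses for recurrence is one candidate. The common time matters: accepting response at any scan while making failure wait would keep early responders and drop early non-responders.

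All other lesions are not evaluable. They are excluded from the section 7.3 response comparisons and counted by reason for exit (request, MR contraindication, death, other). Add a sensitivity analysis that classes lesions by their status at the last available post-radiosurgery scan.

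In section 4.6, state that, where consent allows, clinical post-contrast T1 MRI and pathology already in the record may be used to complete a lesion's status. This will not help every patient who has died or can no longer have MR, so the not-evaluable class is still needed.

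The cost is wording in sections 4.6, 7.1 and 7.3, plus chart review using the medical record numbers that section 6.1 already collects. No scans are added. The downside is slightly fewer lesions in the secondary tests.
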